14.1.3 Reporting and handling of adverse events

All the adverse events and serious adverse events observed in the clinical trial should be clearly filled in the adverse event column of case report form. The duration of adverse event (i.e., the date of occurrence and disappearance of adverse event), severity, relationship with the clinical trial, and corresponding treatment and other handling measures should be recorded. Subjects occurring such event shall be followed up to end of the trial or the adverse event outcome.

14.1.4 Correlation between adverse event and product

The correlation between all adverse events and study interventions must be judged by the investigators. The investigators then assessed based on temporal relationship and clinical experience. The followings are the evaluation criteria and judgment results of correlation:

- (1) The adverse event occurs within a reasonable time after the application of the device;
- 2) The adverse event can not be explained by other reasons;
- 3) The adverse event id relieved or disappeared after the the device is not applied;
- (4) The adverse event reappears after reapplication of the device.

Table 3. Correlation evaluation table

Standard	1)	2	3	4	
Results		_		_	
Definitely related	+	+	+	+	
Probably related	+	+	+	?	
Possibly related	+	-	?	?	
Unlikely related	-	-	?	?	
Unrelated	-	-	-	-	
"+" indicates conformity, "-" indicates non-conformity, "?" Indicates unable to judge					

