7.1 Stapler Information

Product name	ECHELON Flex Powered Articulating Endoscopic Linear Cutters		
Specification/model	PSE45A, PCE45A, PLE45A, PSE60A, PCE60A, PLE60A		
Registration No.	GXZJ 20173226240		
	The product is a sterile device for single patient use, consisting of closing rod, red firing		
	lock, firing handle, anvil release button, lithium battery pack, battery pack-releasing		
Structural	piece, hole cover plate for manual override maintenance, knife-reversing switch, knob,		

composition	articulation fins, reload alignment slot, anvil jaw and reload jaw. The lithium battery pack must be installed prior to use. The product has been sterilized by irradiation. This product is provided for single use.
Applicable scope	The Disposable Powered Articulating Endoscopic Linear Cutter Stapler is intended for transection, resection, and/or creation of anastomoses. The instrument has application in multiple open or minimally invasive general, gynecologic, urologic, thoracic, and pediatric surgical procedures. It can be used with staple line or tissue buttressing materials. The instrument may also be used for transection and resection of liver parenchyma (hepatic vasculature and biliary structures), pancreas, kidney and spleen.
Manufacturer	Ethicon Endo-Surgery, LLC
Agent	Johnson & Johnson Medical (Shanghai) Ltd.

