8.1.4 Measures for reducing and avoiding bias

- (1) Before the start of the study, the sponsor shall provide relevant training for the investigators participating in the study to ensure that the investigators fully understand the study process and are familiar with the operation of the study device; during the study, the investigators shall operate in strict accordance with the operating methods and procedures in the study protocol, and the clinical trial monitor shall do a good job in quality control and monitoring to ensure that the investigators operate and implement in strict accordance with the study protocol. The above measures shall be implemented throughout the implementation phase of the study to reduce errors or operational errors.
- (2) Subjects shall be screened in strict accordance with the clinical diagnostic criteria, as well as the inclusion and exclusion criteria of the trial protocol to reduce selection bias.
- (3) Total laparoscopic digestive tract reconstruction is difficult to operate, which should be carried out in centers with rich experience in laparoscopic surgery. In view of the learning curve of laparoscopic surgery, doctors can be more proficient based on at least 50 cases^[2]. The operating surgeon of laparoscopic surgery is recommended to be experienced in at least 100 cases of open surgery as the operator and 50 cases of laparoscopic surgery as the primary assistant.
- (4) When the clinical trial is completed, the data storage and collation shall be done well. When data problems are found, the data analyst shall check and confirm the data through the data clarification form to avoid recording errors.

8.1.5 Investigational medical device and control medical device or control diagnosis and treatment method

See the corresponding IFU for the diagnosis and treatment method with the investigational medical device and the reference medical device. In addition, subjects may use circular stapler or other types of staplers during the clinical trial. If these staplers are used, the investigators should truthfully record the model of these staplers and staple cartridge for reference.

When subjects experience adverse events related to the stapler, the investigators should truthfully judge the correlation between adverse events and the test device.

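### For postoperative staple-line events, Table 3 cannot return its two highest relatedness ratings and has no row for a well-timed event with no other explanation

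*Combined protocol and SAP*

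**What the plan says.** Section 14.1.4 makes the rating compulsory: "The correlation between all adverse events and study interventions must be judged by the investigators". Section 14.1.3 has the relationship entered on the case report form with each event, and section 8.1.5 adds, for stapler-related events, that "the investigators should truthfully judge the correlation between adverse events and the test device".

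The four criteria in 14.1.4 are:

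1. reasonable timing after use of the device;
2. no other explanation;
3. the event is "relieved or disappeared after the the device is not applied";
4. "The adverse event reappears after reapplication of the device".

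Table 3 turns marks on these criteria (+ met, - not met, ? cannot be judged) into five ratings. Section 14.1.4 gives no default for a pattern that is not listed.

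On the devices, the test stapler is disposable by name (3.2), and the control is described in 7.1 thus: "The product is a sterile device for single patient use". Section 4 explains that staplers of this kind join or transect tissue with titanium staples. The visit schedule in 8.2.7 puts device use in one operation on Day 0, with follow-up only at Days 7 and 30.

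**The concern.** Criteria 3 and 4 ask whether an event stops when exposure stops and returns when exposure resumes. They suit a product that can be withdrawn and given again. A stapler leaves its staples behind. A leak or bleed that starts after the operation begins when the instrument is already out and the staples are still in, so there is no withdrawal to observe and no planned re-exposure.

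What is at stake is the meaning of the relatedness column. If the two highest ratings cannot be given to the postoperative events of most interest, their absence from the listing reflects the scale and says nothing about the device. Where the table gives no answer, investigators have to improvise, and under 8.2.4 they know the allocation. Ratings could then differ between sites or arms for reasons unrelated to the events.

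**Working it through.** There is no stated figure to reproduce; the check is on the logic of Table 3. Its rows are:

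| Rating | 1 | 2 | 3 | 4 |
|---|---|---|---|---|
| "Definitely related" | + | + | + | + |
| "Probably related" | + | + | + | ? |
| "Possibly related" | + | - | ? | ? |
| *Unlikely related* | - | - | ? | ? |
| *Unrelated* | - | - | - | - |

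**All patterns.** Four criteria with three possible marks give 3 × 3 × 3 × 3 = 81 patterns. Table 3 rates 5 of them.

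**Criterion 4 cannot be +.** 3 × 3 × 3 × 2 = 54 patterns remain. The top rating is lost; the other four are still reachable.

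**Neither criterion 3 nor criterion 4 can be +** (the postoperative staple-line case). 3 × 3 × 2 × 2 = 36 patterns remain. The two highest ratings are lost and three are left.

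**Both can only be ?.** 3 × 3 × 1 × 1 = 9 patterns remain, and only "Possibly related" and *Unlikely related* are reachable.

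**Plausible timing and no other explanation.** Criteria 1 and 2 are +, and criteria 3 and 4 are each - or ?. That gives 1 × 1 × 2 × 2 = 4 patterns: + + - -, + + - ?, + + ? - and + + ? ?. None has a row. The closest row to + + ? ? is + - ? ?, which differs on criterion 2. An investigator who uses it records that another explanation exists after judging that none does.

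**Scale.** The documents do not say how often + + ? ? would arise. For orientation only, 14.1.5 cites a literature leakage incidence of 4% to 15%. If that range applied to all 164 subjects, it would mean 164 × 0.04 = 6.6 to 164 × 0.15 = 24.6, or about 7 to 25 leaks over both arms. None could receive either of the top two ratings. The share with no other explanation is unknown.

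**What uses the rating.** The formulas in 8.1.16 count subjects with an AE or SAE whatever the cause, and the bleeding, leakage, stricture and infection rates carry no relatedness filter. Section 8.1.16 item 6 treats anastomosis-related events as serious without reference to Table 3. The SAE reporting rules in 14.2.2 and 22.1 do not depend on relatedness. Section 9.7.1 tests safety indicators between arms and lists adverse events; it plans no analysis by rating. The primary endpoint in 8.1.15.1 has its own attribution rules for conversion and repair.

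**The case against.** Four arguments can be made on the other side.

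*The device is re-fired.* A reader might infer that the stapler acts once and that no event at all can reach the top rating. The documents do not support that. Section 8.1.17 assesses repeated firing, and footnotes 13 and 14 to 8.2.5.5 record use and tissue for each reload. An intraoperative event such as tissue entrapment could stop on withdrawal and recur at the next firing. The plan neither defines that as reapplication nor excludes it. This argument stands for intraoperative events, and it is why the point is restricted to postoperative ones.

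*Competing causes are common.* Section 14.1.5 says leakage may come from the stapler, the patient's condition or the operator, and describes bleeding as generally technical. Criterion 2 will then often be -, and + - ? ? does have a row. This stands as a limit on frequency. It does not supply a row for the events where the investigator finds no other cause.

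*Attribution is captured elsewhere.* Footnote 11 to 8.2.5.5 asks for the reason and the relation to the stapler for conversion, repair, dehiscence and other complications recorded with the intraoperative product observations. For postoperative events, footnote 15 asks only for the grounds on which the event was confirmed. This covers the operation, not the follow-up.

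*Judgement is allowed.* Section 14.1.4 says the assessment rests on timing and clinical experience. It then presents the four criteria and the table as the means of judging, and states no override.

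**Conclusion.** The point holds for leakage, bleeding, stricture and infection arising at the staple line after surgery. For these, two of the five ratings in Table 3 cannot be reached, and all four patterns with plausible timing and no other explanation are unrated.

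A reader might go further and infer that the safety comparison or the trial conclusion is compromised. The documents do not support this: no planned endpoint, test or SAE reporting trigger filters on the rating. The effect is limited to the device attribution recorded and listed for AEs and SAEs. It is still worth correcting, because the rating is required for every event and fails for the clearest postoperative device-caused cases.

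The conclusion rests on three assumptions: criterion 3 means relief because exposure ended, not simply recovery with time; a further firing in the same operation is not reapplication for an event that starts after it; and the five rows of Table 3 were read correctly, which their agreement with the legend supports.

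**What to change.** In 14.1.4, replace criteria 3 and 4, or make them non-mandatory, for this device. Workable substitutes are that the event is located at a staple line made by the randomised device, or that a malfunction or incomplete staple line was observed. Location also helps because 8.1.5 allows circular and other staplers in the same subject.

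Keep criterion 2. Location alone does not separate the device from patient or technique causes, which 14.1.5 names as alternatives.

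Assign a rating to every combination of marks, so that plausible timing with no other explanation is rated at least "Probably related". State whether a repeat firing within one operation counts as reapplication.

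List AEs and SAEs by arm with the revised rating. Keep this descriptive, since the raters know the allocation and no test by rating is planned.

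The cost is new wording in the protocol table and the CRF, and brief site training. No visits or subjects are added.

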14.1.5 Handing protocol of adverse events that may occur in this clinical trial

- (1) Anastomotic bleeding: It is related to the factors of anastomotic leakage. The bleeding is generally the technical factor. The prevention is mainly to avoid the tension at the anastomotic stoma and the fat drop left at the cutting site.
- (2) Anastomotic leakage: The incidence of anastomotic leakage is reported to be 4% to 15% in the literature. It may be caused by the stapler, or related to the patient's condition or the doctor's operation;
- (3) Anastomotic stricture: It is one of the most common complications, mostly occurring after 1 month after surgery.
- (4) Major incisional bleeding: Drop in hemoglobin $\geq 20g/l$ resulting in ≥ 1 transfusion.
- (5) Minor incision bleeding: Bleeding that does not meet the criteria for "severe bleeding".
- (6) Incision site infection: Infection at the incision site due to improper nursing, resulting in prolonged incision healing time, prolonged suture removal time, or unplanned antibiotic therapy.
- (7) Delayed healing of incision: The incision in contact with suture has delayed healing time.
- (8) Anemia and hypoproteinemia: Symptoms caused by tumor deterioration in patients with gastric cancer;
- (9) Tumor recurrence or metastasis: Symptoms caused by further tumor deterioration in patients with gastric cancer;

(10) Gastrointestinal discomfort symptoms: Common symptoms of gastrointestinal diseases, such as nausea, belching, constipation, diarrhea, acid reflux, abdominal pain, etc.

14.1.6 Handing of adverse events that may occur in this clinical trial

The above are foreseeable adverse events of this study. The investigators may treat adverse events according to clinical diagnosis and treatment regulations as needed and record them faithfully.

14.2 Serious Adverse Event

14.2.1 Definition of serious adverse event

Serious adverse event refers to events occur in the process of clinical trial that causes death or serious deterioration of health, including

- (1) Fatal disease or injury;
- (2) Permanent damage to the body structure or body function;
- (3) Requiring hospitalization or prolonging the hospitalization
- (4) Requiring medical or surgical intervention to avoid the permanent damage to the body structure or body function;
- (5) Any event that results in fetal distress, fetal death, or a congenital anomaly or birth defect.

14.2.2 Handling of serious adverse events

- (1) In case of any serious adverse event in the clinical trial, the investigators should immediately take appropriate therapeutic measures for the subjects, report to the management department of medical device clinical trial of the clinical trial institution in written form, and notify the sponsor in written form.
- (2) The management department of medical device clinical trial shall submit a written report to corresponding ethics committee, food and drug regulatory authority, and health commission authority of the local province, autonomous region or municipality directly under the central government where the clinical trial institution is located within 24 hours.
- (3) For death-typed events, the clinical trial institutions and investigators should provide all required data to the ethics committee and the sponsor.
- (4) For serious adverse events and device defects that may cause serious adverse events, the sponsor shall report to the filed food and drug regulatory authority and the health commission authority at the same level within 5 working days after being informed, notify other clinical trial institutions and investigators participating in the trial, and timely notify the ethics committee of the clinical trial institution through its medical device clinical trial management department.

14.3 Reporting and Handling of Device Defects

Device defects refer to unreasonable risks that may endanger human health and life safety under normal use of a medical device during a clinical trial, such as labeling errors, quality problems and failures, etc.

Possible device defects: identification error, product quality problem; design defect; damage of disinfection package, etc.

All device defects are documented on the Device Defect Record form, and device defects that could have led to serious adverse events shall be reported and documented within 5 working days.

15. Device Management

15.1 Study Device Management

Clinical trial institutions shall establish a strict registration system for the distribution of study devices. The sponsor shall assign a special person to directly deliver the study medical devices and control medical devices to each clinical trial institution. Clinical trial institutions and the sponsor shall establish perfect device receiving formalities, and the records shall include the date, quantity, batch number and expiry date. Each clinical trial institution uses a special *Record Form for Use of Medical Devices in Clinical Trials* to register the name of the subject, date of use, and signature of the device administrator, etc.

15.2 Device Packaging

The external package and number of study medical devices shall be unified, and the number, name, specification, course of treatment, production date, shelf life and the words "for clinical study only" shall be indicated on the package.

15.3 Recovery of Remaining Device

Upon termination of the trial, the sponsor will collect all unused study medical devices and control medical devices, and the sponsor is responsible for destroying the unused medical devices. All supplies must be accounted for at the end of the study.

16. Deviations from Clinical Trial Protocol and Provision for Amendments to Clinical Trial Protocol

16.1 Deviations from Clinical Trial Protocol

16.1.1 Definition of protocol deviation

Deviation refers to a situation where the requirements of the clinical trial protocol are not followed intentionally or unintentionally.

16.1.2 Deviation control measures

16.1.2.1 Sponsor

- (1) The protocol shall be clearly described, and possible protocol deviations shall be considered. The protocol shall be designed in a way to minimize the occurrence of protocol deviations, and possible protocol deviations shall be simply and clearly identified and confirmed.
- (2) In the investigator meeting and monitor training of the study project, the implementation details of the protocol, and the reporting and monitoring of protocol deviations should be given intensive training.
- (3) There is a special protocol deviation control group that regularly reviews the protocol deviation records to identify potential trends and system errors; the correction of protocol deviation should be implemented. If it is necessary to immediately amend the protocol or study plan, the study project should be suspended in time, and the study can be continued after the protocol is amended and the retraining is completed.

16.1.2.2 Investigators

- (1) At the project evaluation stage before the start of the study, the study protocol shall be read carefully, and the enforceability of the protocol in the institution shall be fully discussed with the sponsor.
- (2) The investigators are responsible to explain the importance of compliance with the protocol to the subject at the time of informed consent.
- (3) The investigators shall comply with the protocol approved by the Ethics Committee. In addition, the occurrence of protocol deviation should be recorded and explained immediately when he/she recognizes it.

16.1.3 Retraining

In the following cases, the investigators must receive re-training, and may receive multiple trainings if necessary.

- (1) There are deviations in the understanding of the protocol;
- (2) There are new investigators participating in the trial;
- (3) The study plan changes;
- (4) The investigators are reminded of the protocol details.

16.1.4 Protocol deviation report

In case of any deviation from the clinical trial protocol that affects the rights, safety and health of the subjects or the scientificity of the clinical trial, including the requested deviation and the reported deviation; the investigators should timely report to the management department for medical device clinical trial of the clinical trial institution, and timely notify the sponsor and the Ethics Committee to determine whether the

trial can continue to be conducted.

In order to protect the rights, safety and health of subjects, where the deviation occurs in an emergency can not be reported in a timely manner, it shall be reported in written form as soon as possible afterwards in accordance with relevant regulations.

During the clinical trial, in case of revising the clinical trial protocol, informed consent form and other documents, requesting for deviation and resuming the suspended clinical trial, the implementation can only be continued after obtaining the written approval from the Ethics Committee.

The investigators should strictly follow the clinical trial protocol. Without the approval of the sponsor and the Ethics Committee, or failing to obtain the approval from NMPA (original CFDA) as required, the investigators should not deviate from the protocol or materially change the protocol. However, in the event of an emergency that requires immediate removal, such as when the subject is at an immediate risk, a written report may be made afterwards.

16.2 Amendments to Clinical Trial Protocol

Medical device study protocol should be based on the primary principle of protecting the rights, safety and health of the subjects to the maximum extent. It should be jointly designed and formulated by the medical institution responsible for the clinical trial and the sponsor, and should not be implemented until recognized by the Ethics Committee; if the investigators have any revision to the study protocol, informed consent form and case report form during the study, the clinical trial should not be continued until approved by the Ethics Committee.

17. Direct Accessed Source Data/Source Documents

The authorized monitor has the right to access and verify the source data/documents of the subjects, so as to judge whether the investigators conduct the clinical trial according to the requirements of the protocol, and whether the source data/documents are timely recorded in the subject medical records. The monitor should confirm that the source data/documents are traceable and verifiable. Meanwhile, the data filled in the CRF should correspond to the source data/documents.

When any personnel participating in the clinical trial question the clinical trial data, the investigators shall timely provide the source data/source documents for verification by relevant personnel and carefully reply to the relevant queries.

Source data/documents should be properly kept in accordance with the requirements of relevant laws and regulations. Prior to destruction, it shall be signed and confirmed by the sponsor, and comply with relevant laws and regulations.

18. Finance and Insurance

The sponsor of this clinical trial is responsible for providing the investigational medical device and control

medical device required by this clinical trial, and providing the inspection item cost required by this clinical trial. The sponsor shall bear the treatment cost and corresponding economic compensation for the subjects who suffer from injury or death related to the clinical trial, except for the damage caused by the faults of medical institutions and their medical staff in the diagnosis and treatment.

The specific requirements for finance and insurance are detailed in the relevant agreements.

Medical accidents refer to accidents in which medical institutions and their medical staff violate the laws, trial protocols and guidelines for medical and health management in medical activities, and negligence results in personal damage to patients.

19. Contents Covered in Clinical Trial Report

The clinical trial report shall be prepared in accordance with relevant requirements of GCP and with reference to *Template for Clinical Trial Report of Medical Devices*, including but not limited to:

- (1) General information;
- (2) Abstract;
- (3) Introduction;
- (4) Clinical trial purpose;
- (5) Clinical trial method;
- (6) Clinical trial content;
- (7) General clinical data;
- (8) Investigational medical device and control medical device or control diagnosis and treatment method;
- (9) Statistical analysis method and evaluation method adopted;
- (10) Clinical evaluation criteria;
- (11) Organizational structure of clinical trial;
- (12) Ethical statement;
- (13) Clinical trial results;
- (14) Adverse events identified in clinical trials and handling situations;
- (15) Analysis and discussion of clinical trial results, especially indications, applicable scope, contraindications and precautions;
- (16) Clinical trial conclusion;
- (17) Existing problems and suggestions for improvement;
- (18) List of trial personnel;
- (19) Other situations requiring explanation.

20. Confidentiality

The investigators must strictly keep confidential the study results, protocol and other data, and can not release

them by themselves unless authorized by the sponsor in written form. If referenced, a written authorization must also be obtained from the sponsor in advance.

All personal information of subjects is confidential. Besides relevant study personnel, only the sponsor, ethics committee members and relevant national/local food and drug administration personnel related to this study project can be allowed to access such information. The investigators and sponsor should keep the personal information of the subjects confidential.

21. Agreement on Publication of Study Results

The sponsor and investigators shall agree with the final study report.

The results of the study may be made publicly available as scientific literature and the results may be submitted to authorities. This clause is intended to protect trade secret materials.

All information about the study medical device (e.g., patent application, previously undisclosed manufacturing process provided to the investigators by the sponsor, basic scientific data, etc.) is considered confidential and its ownership belongs to the sponsor. The investigators may not use it for other purposes without the written permission of the sponsor.

Prior to publication or presentation of the results of this study, the investigators allow the sponsor to review the manuscript and comment within 30 days to confirm that the confidential information is not disclosed, and to supplement the relevant information. According to the generally accepted principles of scientific cooperation, the investigators should discuss the manuscript with the relevant personnel of the sponsor and reach a consensus before the manuscript is published.

22. Responsibilities Assumed by Each Party

